6.2 IMPORTANT PROTOCOL VIOLATIONS

Due to the fact that this is a phase I/II study, no per protocol population is needed, however important protocol violations should be identified for patients in the treated set both for phase I and II (any protocol violation which may affect safety or efficacy evaluation).

Table 6.2: 1 Description of PVs

[figure not shown]
Category/ Code		Description	Comment/Example	Efficacy (E) / Safety (S) / Patients right (R)
A		Inclusion/Exclusion Criteria		
A1		Criteria related to safety		
A1.1		Patient has condition that may cause additional risk from study medication	IN 4, Ex 4, 6, 7, 15	S
A1.2		Patient has laboratory assessments that may cause additional risk.	Ex 8-11	S
A1.3		Patient is unable to comply with the protocol	IN 5, Ex 13. Ex 18	S
A1.4		Patient has condition that may interfere with evaluation of safety (and/or efficacy)	Ex 5, Ex 12, Ex 14	S
A2		Criteria related to efficacy		
A2.1		Patient does not have trial diagnosis or is not part of the target population	IN1-3, 6, Ex 1-3	E
B		Legal criteria		
B1		Informed consent not given or after visit 1	IN7	R
B2		Men or women who are sexually active and not using adequate contraception.	Ex 16	R
B3		Pregnant or nursing female patient	Ex 17	R
C		Administration of trial medication not in accordance with the protocol		
C1		Administration of trial medication not in accordance with the protocol	As marked on the eCRF	
C2		Continuation of treatment although criteria for re-treatment are not met	Create listing, decision at DQRM/RPM, see CTP section 4.1.4	
C3		Unjustified intra-patient dose-escalation	Create listing, decision at DQRM/RPM, see CTP section 4.1.4	

Category/ Code		Description	Comment/Example	Efficacy (E) / Safety (S) / Patients right (R)
	C4	Withdrawal of patient not performed according to CTP	Create listing, decision at DQRM/RPM, see CTP section 6.3	
	C5	Discontinuation of trial drug not performed according to CTP	Create listing, decision at DQRM/RPM, see CTP section 6.3	
D	Restrictions			
	D1	Additional experimental anti-cancer, chemo-, immuno-, hormone - or radiotherapy during the study or too shortly before the study.	Create listing, decision at DQRM/RPM	E
E	Missing data			
	E1	Baseline bone marrow assessment not within 14 days prior to first treatment	Create listing, decision at DQRM/BPRM	E
	E2	Missing disease assessment at a time point where disease assessment was required	Create listing, decision at DQRM/BPRM	E

6.3 PATIENT SETS ANALYSED

Two analysis populations are defined according to the different trial phases for both the efficacy and safety analyses. For the phase I part the treated set (phase I) is defined, in analogy to the intention to treat population as the treated set with respect to phase I; i.e. all patients of phase I who have received at least one single dose of either BI 6727 or cytarabine will be considered, including the patients who have been replaced for any reason.

For the phase II part the treated set (phase II) is defined, in analogy to the intention to treat population as the treated set with respect to phase II; i.e. all patients of phase II who have received at least one single dose of either BI 6727 or cytarabine will be considered, No per protocol population will be used for analyses. However protocol violations will be described.

6.5 POOLING OF CENTRES

All centres will be analyzed together, with any centre effects being ignored. Country or region effects will also not be considered. This means that the patient sets analysed will be defined without taking into account the centre a patient comes from.

For the primary endpoint in phase II (objective response) any centre effects will be analysed descriptively if necessary.

6.6 HANDLING OF MISSING DATA AND OUTLIERS

Missing or incomplete AE dates are imputed according to BI standards ([\[3.\]](#))

Missing data and outliers of PK data are handled according to [\[1.\]](#).

If not stated otherwise, missing data will not be imputed and remain missing. Potential outliers will be reported and analysed as observed.

ECOG Performance Score

In case that the very last ECOG score is missing the ECOG score with the latest date available will be used if the latest date is after baseline. Otherwise ECOG remains missing.

Laboratory values, vital signs:

In case of missing data at visit 1 (before very first administration of BI 6727), the data of preceding visits will be used if not obtained longer than seven days before treatment course 1.

Missing of dates:

Dates that must have taken place before informed consent (e.g time of first cytological diagnosis)

If (only) the day is missing then day 15 will be imputed except if day 15 is later than the informed consent day, then the date of informed consent will be imputed.

If the month is missing (additionally to the day) then July 1st will be imputed except if July 1st is later than the informed consent month, then the month of informed consent will be imputed.

Other dates

For other dates, if the day is missing then day 15 will be imputed. If the month is missing then July 1st will be imputed.

Missing PHYSDT:

In general if a physdt is missing (e.g. for ECOG or weight) the corresponding visdt will be used. Since visdt will not be cleaned such imputations need to be examined for appearing impossible results.

Missing of infusion time:

If the time of infusion is missing, then the start time of the infusion will be imputed as "0:00" and the stop time will be imputed as "1:00".

Missing administration times LD-Ara-C:

If the start time of the first injection is missing, then the start time of the injection will be imputed as "0:00" If the stop time of the last injection is missing the new stop time is 23:59.

Start and end dates of concomitant therapies:

The dates will be imputed such that the extent of exposure to concomitant therapy is maximal, i.e. the first day (month) of the month (year) for incomplete start dates and the last day (month) of the month (year) for incomplete end dates.

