5.2.4 Eastern Cooperative Oncology Group (ECOG) performance score

ECOG score: as given on the eCRF.

ECOG score change from baseline to last visit of last course = ECOG score at last visit of the last course – ECOG score at baseline. See also section [6.4](#) for missing ECOG scores.

Categorical ECOG score change: The ECOG score changes from baseline score will be categorized on a three point categorical scale: deteriorated (-1), unchanged (0), and improved (1). Improvement or deterioration of performance status will require a decrease or an increase from baseline, respectively, of at least one point on the ECOG scale.

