7. PLANNED ANALYSIS

For in-text tables, the set of summary statistics is: N (number of patients with non-missing values), mean, standard deviation (SD).

For end-of-text tables, the set of summary statistics is: N / Mean / SD / Min / Median / Max.

For appendix tables, the set of summary statistics is: N / Mean / SD / Min / Q1 (lower quartile) / Median / Q3 (upper quartile) / Max.

Tabulations of frequencies for categorical data will include all possible categories and will display the number of observations in a category as well as the percentage (%) relative to the respective treatment group. Percentages will be rounded to one decimal place. The category missing will be displayed if and only if there are actually missing values. Percentages will be based on all patients in the respective patient set whether they have non-missing values or not.

In general all analyses will be performed for the treated set (phase I) and the treated set (phase II) separately. No pooling across these two treated sets will be performed unless noted otherwise.

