7.5 SECONDARY ENDPOINTS

Event-free survival (EFS)

EFS will be analyzed with the Kaplan-Meier method for each of the treatment arms as well as overall treatments. An exploratory (non-stratified) logrank test will be used to compare the different treatment arms. For phase II Kaplan-Meier curves for EFS in the genetic subgroups defined in [Section 6.4](#) will be presented separately.

The percentage of patients who are event free will be displayed at monthly or greater time intervals as appropriate.

Patients for whom no leukemia assessment is available within 42 days prior to discontinuation from treatment will be examined on a case by case basis. A listing will be provided.

Overall survival

Overall survival will be analyzed in a manner similar to that of event-free survival.

Remission duration

Remission duration will be summarized by treatment group. Kaplan-Meier plots of the relapse-free survival will be displayed without displaying hazard rates, associated confidence intervals and p-values. Expected duration of response will be calculated based on an exponential model if appropriate.

Note that for remission duration no formal comparison between different treatment arms will be done since remission duration is based on a non-randomised set and therefore possibly biased.

ECOG performance score

The proportion of patients with improved (decreased), and with unchanged, ECOG at end of treatment with respect to baseline will be tabulated.

BI 6727 plasma concentration

See section [7.7.5](#)

Incidence and intensity of adverse events graded according to CTCAE

See section [7.7](#)

Pharmacodynamic monitoring

Analysis of pharmacodynamics will be performed separately and will not be contained in the CTR.

Pharmacogenetics

Analysis of pharmacogenetics will be performed separately and will not be included in the CTR.

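### SAP 6.6 carries the last ECOG score past death, so a patient who dies in course 2 or later can be tabulated as unchanged or improved at end of treatment

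*SAP*

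**What the plan says.** The general rule in SAP 6.6 is that missing data are not imputed unless stated otherwise. ECOG is one of the stated exceptions: "In case that the very last ECOG score is missing the ECOG score with the latest date available will be used", on condition that this date falls after baseline; failing that, the value stays missing. Death is not mentioned.

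SAP 5.2.4 defines the variable: "ECOG score change from baseline to last visit of last course = ECOG score at last visit of the last course", less the baseline score. It sorts the change into deteriorated, unchanged and improved: "Improvement or deterioration of performance status will require a decrease or an increase from baseline, respectively, of at least one point on the ECOG scale".

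SAP 7.5 describes the table: "The proportion of patients with improved (decreased), and with unchanged, ECOG at end of treatment with respect to baseline will be tabulated". Deteriorated is not named there.

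Two general rules in SAP section 7 also apply. "Tabulations of frequencies for categorical data will include all possible categories". "Percentages will be based on all patients in the respective patient set whether they have non-missing values or not". A missing category is shown whenever values are missing.

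The protocol schedules ECOG at screening (6.2.1.1), at visit 1 (6.2.2.1) and visit 7 (6.2.2.7) of each cycle, at the end-of-treatment visit (6.2.3.1) and at follow-up visits (6.2.3.2). Visits 2 to 6 have none. The SAP's course is the protocol's cycle.

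**The concern.** A patient who dies in mid-course has no visit 7 score for that course and may have no end-of-treatment score. The score is missing because the patient died, yet the SAP fills the gap with a value recorded while the patient was alive. The table then presents that value as status at end of treatment.

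This differs from how the SAP treats death elsewhere. Death before any assessment counts as progressive disease for best overall response (5.1.2). Death shortens exposure time (5.3.2) and ends the analysing treatment period (6.1.3). Where a visit has several ECOG values, the worst is taken (6.8). Only for ECOG after death does an earlier and possibly better value stand.

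Death on treatment is foreseeable, since protocol 1.4 calls the risk of a fatal outcome within a year of diagnosis high. If such deaths differ in number between the arms, the ECOG table can make performance status look more stable in the arm with more of them. Nothing in the table would show the reader that this had happened.

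**Working it through.** The documents give no ECOG result or expected rate, so there is no figure to reproduce. The check follows the rules through by time of death and then gives the size per patient.

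**Step 1: which score is used.** Baseline is the value on the day of first administration, or the latest before it (SAP 6.7). That is normally the visit 1 score of course 1.

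| Death occurs | Latest score under SAP 6.6 | Class in the table |
|---|---|---|
| Course 1, before visit 7, no end-of-treatment score | None after baseline | Missing, but kept in the denominator |
| Course 2 or later, before visit 7, no end-of-treatment score | Visit 1 of that course, or visit 7 of the one before | Improved, unchanged or deteriorated, by the pre-death score |
| After an end-of-treatment assessment | End-of-treatment score or the scheduled last score | By a score actually taken at that point |

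Only the second row is affected, and within it only patients whose carried score is no worse than baseline.

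**Step 2: size.** Inputs:
- N = 43 patients per phase IIa arm (protocol 7.6.2).
- d = deaths in course 2 or later with no later ECOG score. This is an assumption; the documents give no figure.
- q = share of those deaths whose carried score is no worse than baseline. This too is an assumption.

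Overstatement of the improved plus unchanged proportion = d × q / N.

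Per qualifying death: 1/43 = 2.3 percentage points.

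| d | q | d × q / 43 | Overstatement (points) |
|---|---|---|---|
| any | 0 | 0/43 | 0 |
| 2 | 0.25 | 0.5/43 | 1.2 |
| 4 | 0.50 | 2/43 | 4.7 |
| 6 | 0.75 | 4.5/43 | 10.5 |
| 9 | 1.00 | 9/43 | 20.9 |

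Fractional counts are expected values. The last line is a ceiling, with every carried score no worse than baseline.

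The distortion of the difference between arms is the difference of the two arms' values of d × q / 43. If both arms have the same d and q, it is zero.

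**Step 3: the tabulation wording.** SAP 5.2.4 has three categories and SAP 7.5 names two. Section 7 asks for all possible categories, a missing row where needed, and all patients in the denominator. Read together, a deteriorated row is already due, and 7.5 is an incomplete sentence. Adding that row does not change Step 1: a death with a carried score no worse than baseline still falls under unchanged or improved.

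**The case against.** The strongest case against is that the table carries little weight. ECOG change is not in the protocol's list of secondary endpoints (2.3), although the SAP places it among them. All analyses are descriptive and exploratory (SAP 3.3), and SAP 7.5 plans no test on ECOG. Deaths are counted in overall and event-free survival. Last status on treatment is also a recognisable summary, and the SAP uses a similar one for laboratory values (5.2.7). The exposed group is narrow too: protocol 6.2.3.1 and 6.3 ask for end-of-treatment information, including ECOG, when a patient stops, so someone who stops for progression and dies later should normally have a score. All of this stands and limits the point to a minor one. It does not justify a rule that reports a dead patient's earlier score as status at end of treatment.

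A reader might infer more than the documents support:
- **That all later-course deaths are reported as stable or improved.** A carried score at least one point above baseline is classed as deteriorated under SAP 5.2.4. Nor does starting another course show that the score was no worse than baseline, because the criteria in protocol 4.1.4 concern progression, blood counts and tolerability and include no ECOG threshold.
- **That the SAP suppresses the deteriorated class.** SAP 7.5 omits it, but section 7 requires it.
- **That course 1 deaths flatter an arm.** Those without a post-baseline score are missing but stay in the denominator, so they do not raise the improved or unchanged percentage.
- **That the combination arm gains.** The documents give no basis for predicting which arm has more such deaths.

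One caveat: SAP 5.2.4 points to section 6.4 for missing ECOG scores. That section is not in the text available for review, and SAP 7.4.1 and 7.5 describe it as defining genetic subgroups. The pointer is probably out of date, with 6.6 the section meant.

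**Conclusion.** The point holds as a minor one. As written, SAP 6.6 lets a patient who dies during course 2 or later, with no end-of-treatment score, be tabulated as unchanged or improved. The size is about 2.3 points per such death in an arm of 43, and nil where the carried score is already worse than baseline. Any total for an arm depends on d and q, which the documents do not give; the range of 1.2 to 20.9 points is illustrative and its top end is a ceiling. The direction of any effect on the comparison between arms is unknown. The mismatch between SAP 7.5 and SAP 5.2.4 and section 7 is a separate wording inconsistency. It should be settled in the same edit, but it is not evidence that deterioration would go unreported.

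**What to change.** In SAP 5.2.4 and 6.6, state that no ECOG score is carried forward past an on-treatment death, meaning a death before the post-study start defined in SAP 6.1.1. Correct the pointer to section 6.4 if 6.6 is meant.

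In SAP 7.5, list the rows by arm as improved, unchanged, deteriorated, died on treatment and missing, with all treated patients as the denominator. Deaths get their own row and are not counted as improved or unchanged. Course 1 deaths then move from missing to the same row, so early and late on-treatment deaths are handled alike. Counting death as deteriorated would be a possible alternative, but that makes the class a composite; a separate row avoids this choice.

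The cost is a sentence in the rules and a revised line in 7.5 that adds one row beyond those section 7 already requires. No new data are needed, since death dates are collected for overall survival (SAP 5.2.2). The reported ECOG results may become slightly less favourable.

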6.2.3.2 Follow-up visit

Follow-up visits will be performed after the EoT visit in case patients are not eligible for further treatment cycles until death, lost to follow-up or agreement between sponsor and coordinating investigator not to pursue further follow up visits. Follow-up visits should be performed at 12 weeks intervals or earlier if appropriate. Follow-up visits may also be performed by telephone interview in case the patient is unable to visit the investigator. The following will be obtained and / or performed.

- ! ECOG performance score

- ! AEs since last visit in case they occurred during the observational period (6 weeks after the last trial drug administration) or are considered drug-related (see [5.2.1](#) and [8.4.1](#))
- ! Follow-up of AEs in case they were not yet recovered at EoT
- ! Outcome: date death (if applicable), date of progression (in case, the patient experienced PD)
- ! Treatment with any other antileukaemia drug (report date of treatment and drug)

After approval of Protocol Revision I, Follow-up is completed 21 days after discontinuation of study drug.

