5.2 SECONDARY ENDPOINTS

5.2.1 Event free survival

Event-free survival (EFS) [days] is the shortest duration of the following:-

- dates of assessment indicating 'progressive disease' on RESPONSE page of eCRF – date of randomisation + 1day,
- dates of assessment indicating 'clinical progressive disease' on DISEASS or RESPONSE-page of eCRF – date of randomisation + 1day,
- dates of assessment indicating 'progressive disease' on PAT_STATUS of eCRF – date of randomisation +1 day (for patients who have not been censored before, see below)
- death date – date of randomisation +1day.

Date of assessment refers here to the progt as given in the eCRF. If progt is missing then the corresponding examdt will be taken instead if available. Progression events are only taken into account if the corresponding date is before the start date of a new anti-leukemia therapy (see below for censored patients).

Patients not being assessed 'progressive disease', clinical progressive disease' or death during the trial will be censored as described below. These patients must be reviewed on a case by case basis by the trial statistician (TSTAT) and trial clinical monitor (TCM).

Right censoring rule for event-free survival (EFS):

Patients getting a new additional other anti-leukemia therapy recorded at the eCRF (follow-up) but not being assessed 'progressive disease', clinical progressive disease' or death before the new anti-leukemia therapy was started will be censored at the date of last disease assessment before the new anti-leukemia therapy was started (excluding follow-up).

Event-free survival censored [in days] is the time from randomisation to the date of last visit (Date of last visit (including follow-up) – date of randomisation + 1 day) for all other patients not being assessed 'progressive disease', clinical progressive disease' or death at the time of data base lock. Date of last visit does not include visit dates from follow-up where 'lost to follow-up' = yes.

EFS will be reported in days.

Patients without any response assessment (best overall response = no assessment) and without death will be censored with an EFS of 0. Otherwise the death date will be used.

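### SAP 6.6 leaves imputed dates other than pre-consent dates unbounded; if death and new-therapy dates fall there, survival times can become impossible and a documented EFS progression can be dropped (minor)

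*SAP*

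**What the plan says.** SAP 6.6 has separate rules for several kinds of incomplete date. AE dates follow a company standard, and concomitant-therapy dates are set to give the longest exposure. Dates that must precede consent get a mid-month value with a cap: "If (only) the day is missing then day 15 will be imputed except if day 15 is later than the informed consent day", in which case the consent date is used. For the rest the text is "For other dates, if the day is missing then day 15 will be imputed" and "If the month is missing then July 1st will be imputed". No cap or floor is attached to that last rule.

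The dates feed the time-to-event endpoints as follows.

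- **EFS (SAP 5.2.1).** "Progression events are only taken into account if the corresponding date is before the start date of a new anti-leukemia therapy". A patient who starts new therapy with no earlier progression or death is censored at the last on-study disease assessment before that therapy. For progression there is a fallback: "If progt is missing then the corresponding examdt will be taken instead if available".
- **OS (SAP 5.2.2).** Death date minus randomisation date plus one day, with no comparison against other dates.
- **Source of the dates (Protocol 6.2.3.2).** After treatment, death, progression and new therapy are collected at follow-up about every 12 weeks. "Follow-up visits may also be performed by telephone interview in case the patient is unable to visit the investigator".

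**The concern.** Partial dates are foreseeable when death or later treatment is learned of by telephone weeks afterwards. The SAP guards against impossible values for pre-consent dates but not for the dates that define survival times. Two errors follow from the text:

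1. A death imputed to day 15 or 1 July can land before a visit the patient attended, or before randomisation. OS is then too short or negative.
2. A new-therapy start imputed to day 15 or 1 July can land on or before a progression that really came first. The condition in SAP 5.2.1 is strict, so the progression is discarded and an event becomes a censored time.

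SAP 7.5 plans Kaplan-Meier curves and exploratory logrank tests for EFS and OS. With 43 patients planned per arm, a few misplaced or misclassified times could be visible.

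**Working it through.** The plan states no figure to reproduce: neither an expected number of partial dates nor an event count for EFS or OS. Everything below is conditional on a date being partial.

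**Which dates are covered.** Death, progression and new anti-leukaemia therapy are not AE dates, not pre-consent dates and not named under concomitant therapy. The residual rule is what remains. This is inference, not a statement in the SAP.

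**Pairs within one 30-day month, day of the later date missing.** Ordered pairs of distinct days: 30 × 29 / 2 = 435.

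- Progression then therapy. Therapy is imputed to day 15. The progression fails the strict test if it is on day 15 or later, so both days lie in 15–30 (16 days): 16 × 15 / 2 = 120. 120/435 = 27.6%.
- Visit then later death. Death is imputed to day 15. It precedes the visit if the visit is on day 16 or later, so both days lie in 16–30 (15 days): 15 × 14 / 2 = 105. 105/435 = 24.1%.

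**By gap between the two dates.** The SAP 6.6 rule was applied to the later date, taken in turn as each of the 365 days of a non-leap year (uniform), with the earlier date exact.

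| Gap (days) | Death before last visit, day missing | Death before last visit, month missing | Progression lost, therapy day missing | Progression lost, therapy month missing |
|---|---|---|---|---|
| 3 | 40.8% | 49.3% | 44.1% | 49.6% |
| 7 | 27.7% | 48.2% | 31.0% | 48.5% |
| 14 | 4.9% | 46.3% | 7.9% | 46.6% |
| 28 | 0% | 42.5% | 0% | 42.7% |
| 84 | 0% | 27.1% | 0% | 27.4% |

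The shift is −16 to +14 days when the day is missing (mean absolute 7.6) and −183 to +181 days when the month is missing (mean absolute 91). Since the largest backward shift for a missing day is 16 days, a gap above 16 days cannot be reversed when only one date is partial. If progression and therapy are both partial in the same month, and both are imputed by this rule, they receive the same date and the strict test always fails.

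**Worked cases.**

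- Randomised 22 March, died 30 March, day missing: imputed 15 March, OS = 15 − 22 + 1 = −6 days (true 9).
- Randomised 6 September, died 20 November, month missing: imputed 1 July, OS = −66 days (true 76).
- Randomised 4 January, last visit 26 March (day 82), died 30 March, day missing: OS = 71 days (true 86), which is before the last visit.
- Randomised 4 January, progression 18 March (event, day 74), new therapy 25 March, day missing: therapy imputed to 15 March and the progression is ignored. If the last assessment before that was 1 March, the patient is censored at day 57.

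**With bounds.** If an imputed death may not precede the last date known alive, and an imputed therapy start is at least the day after a documented earlier progression, both errors fall to 0 of 365 at every gap in the table, for a missing day and for a missing month. A bound at the progression date itself would only create a tie and would rescue none of the 120 pairs.

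**The case against.** **Scope is inferred.** SAP 6.6 does not name these dates under the residual rule, and SAP 5.2.2 limits the OS event formula to patients whose death date is known. That stands as a caution. The alternatives leave gaps too. If a partial death date counts as unknown, a patient known to be dead fits neither OS formula. If new therapy follows the concomitant-therapy rule, its start moves to the first of the month or to January, which loses more progressions.

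**There are safeguards.** SAP 5.2.1 replaces a missing progression date by the exam date, and asks the trial statistician and clinical monitor to review patients without a recorded event case by case. Protocol 5.8 provides for data quality meetings and queries, and SAP 5.2.3 notes that two related intervals should be positive. A reader might infer that nothing in the plan would detect an impossible date; that is too strong. These steps may catch some cases. But the fallback does not say whether a partial date counts as missing and does not help when the therapy date is the partial one. The EFS review has no criteria and no counterpart for OS. None of these steps sets a bound.

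**The percentages are conditional.** They need a partial date and two dates close together. A reader might infer from the 12-weekly follow-up that the missing-day error is larger there. The table shows the opposite: at 84 days only a missing month matters.

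**Low stakes.** EFS and OS are secondary, and both documents call all analyses descriptive and exploratory. That stands and sets the severity.

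**Conclusion.** The point holds as a minor one. The rule as written can give shortened or negative OS and can turn a documented progression into a censored EFS time. For two dates in one 30-day month with the day of the later one missing, the proportions are 24% (strictly later deaths) and 28%. A missing month can misplace a date by up to about six months. These figures assume uniform dates and apply only to patients with a partial date; the documents do not give that number.

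Two stronger readings are not supported. First, a partial death date does not by itself turn an EFS event into a censored time, because a true death cannot precede new therapy. Its imputation can shorten the time, make it negative, or place death before the therapy and so turn a censored time into an event. Second, nothing shows an effect on the phase II primary endpoint: objective response (CR or CRi) is not directly driven by these dates.

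**What to change.** In SAP 6.6, name death, progression and new anti-leukaemia therapy dates and add:

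1. **Death.** An imputed date is no earlier than the last date known alive, not before randomisation, and no later than the date the death was reported or database lock.
2. **Progression.** A partial date takes the exam date under SAP 5.2.1. If there is none, the imputed date lies between the day after the last progression-free assessment and the report date.
3. **New therapy.** An imputed start is no earlier than the last trial dose. Where the record shows, or is compatible with, progression coming first, it is no earlier than the day after the documented progression. This applies whether the day or the month is missing.
4. **Transparency.** List all patients with imputed event or therapy dates. Where the true order is unknown, item 3 favours counting the event, so repeat EFS with the opposite order as a sensitivity analysis.

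The cost is a few lines of SAP text, simple programming and one listing. The sensitivity analysis is needed only if such patients exist.
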